### **9.3 Procedures at each visit**

#### **9.3.1 Screening/First visit**

Screening visit, Day 0: The potential participants will be given the Patient Information and Informed Consent form. The trial will be explained including how many visits are expected as well as the type of testing that they will complete. They are given time during the appointment to read the information and decide whether to participate in the study. If they choose to not take part in the study, they will not sign the consent form, and the appointment will finish. If they choose to join the trial, they will sign and date the consent form. No trial activities will be performed before the consent form is signed and dated by the subject and the investigator. Subjects will receive a copy of the signed consent form. A hearing history is then taken, and otoscopy is performed. A hearing test is performed, and inclusion/exclusion criteria will be determined. The subject is then randomized regarding the assignment of the music programs (IP or SP) to program slots 2 or 3. They are fitted with the IMD based on a first fit in the software and adjusted using REM data to match the gain targets. The hearing aids will be fit only with a general program in the P1 slot. They will perform the lab test with the AMP in two conditions: unaided and aided with the general program. They are given an IFU for the hearing device. They are given a product questionnaire and a music perception questionnaire and instructed to complete them at home a day before their next appointment. Any AEs are reported in the CRF. They are scheduled for the second visit.

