## **6.1 Methods of minimising bias**

### **6.1.1 Randomization**

A randomized assignment of the position of SP and IP will be used for the field trial period that includes P2 and P3 and consequently the lab tests. The position of the SP and the IP (as either program 2 or 3) will be based on a list created by the statistician. This reduces bias by using a different scroll position as the earlier position has a better chance of scoring higher due to the more prominent placement and likelihood that subjects might not always scroll to the 3rd program. The randomization list will not be concealed from the PI but should be in the ISF so that the PI knows in which condition order to test each subject.

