### **7.3 Assignment to study groups**

For the field tests the allocation is a randomized single-arm design, meaning that all participants will receive the test program (IP) and the comparator (SP). Half of the test subjects will have the SP assigned to the second program position and half to the third with a possible maximum imbalance of 2.

For the adaptive music perception test in the lab, the assignment to the test condition order will follow the randomization of the field test. The subjects will perform the lab test with P2 at visit 2 and P3 at visit 3. Because the assignment to P2 and P3 is randomized it will automatically randomize the test condition order. This will minimize bias created when one test condition is tested in the final or last position all the time.

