### **7.4 Criteria for withdrawal / discontinuation of participants**

Participants are allowed to withdraw from the study at any time and for any reason. They do not have to share the reasons with the investigator. They will be asked to return the IMD. If the decision to withdraw is made by the investigator, the PI will inform the subject in person that they are no longer needed for the study. Reasons for withdrawing a participant from the study could be for non-compliance during testing, unreliable responses, medical reasons such as an ear infection, or the study may need to be stopped or postponed. Any data gathered from these subjects will be used for the current study. All data will remain encoded because results are only recorded using the identification code of the subject. There are normally at least five “back-up” test participants on the list to replace those that withdraw or are withdrawn. The “back-up” participants will have already been screened and deemed to be appropriate for the study.

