#### **9.3.2 Fitting/Second visit**

Fitting Visit, Day 10 +/- 7: Otoscopy is performed, and the subjects return the completed questionnaires. The IMDs are fitted with IP and SP as specified by the randomization carried out at the first visit. The IP is optimized and fine-tuned based on comments that the subject makes about the sound while they play their instrument in the clinic. The SP is programmed without any adjustment based on the default music program offered in the software. They are instructed to switch between programs two and three when playing and listening to music for the next 10 +/- 7 days. They perform the lab test with the AMP in one condition: aided with P2. The subjects are given the music perception questionnaires and instructed to complete them at home a day before their next appointment. One questionnaire pertains to P2 and the other to P3. Any AEs are reported in the CRF. They are scheduled for the third visit.

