3.2 Randomization

The study is based on repeated measures with the SP and the IP. Participants are asked to switch between the listening programs in a given condition (practice, rehearsal, or concert) in order for them to gather comparable experiences while playing and listening to music.

Program allocation effect, i.e. higher likelihood to use program 2 than 3, will be compensated by randomizing the order of the tested protocols in the listening program slot. This risk is outbalanced by the benefit of directly comparing the same listening situation with both programs.

The program order will be randomized, and the lab test order will follow the program order randomization. The active participation of the investigator is required for the IP resulting in a single blind (participant only) design. The randomization list will be provided to the investigator by the statistician and documented before the recruitment process starts.

The randomization list will be generated with a random permuted block method and a random digit link to control any potential order inequality. Pocock (1983, p 77) provides a link between random digits and the structure of blocks for four patients and 2 treatments (order). No stratification is foreseen because no confounding factors have been identified at this stage of the study design.

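### Program slots are drawn at visit 1 from a list open to the investigator but first used at visit 2, so the stated maximum imbalance of 2 can be exceeded among those fitted

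*Protocol*

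**What the plan says.** **Timing.** At visit 1 (Protocol 9.3.1): "The subject is then randomized regarding the assignment of the music programs (IP or SP) to program slots 2 or 3". In the same visit, "The hearing aids will be fit only with a general program in the P1 slot", and the music perception (AMP) test is run unaided and with that program. The schedule table, printed both in the Study Schedule and in 9.1, also puts randomisation at visit 1. The allocation is first used at visit 2 (Protocol 9.3.2): "The IMDs are fitted with IP and SP as specified by the randomization carried out at the first visit".

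**Access to the list.** Protocol 6.1.1: "The randomization list will not be concealed from the PI but should be in the ISF". Protocol 6.2 repeats that the investigator has access. SAP 3.2 has the statistician give the list to the investigator and explains the single blinding: "The active participation of the investigator is required for the IP resulting in a single blind (participant only) design". The same investigator answers enquiries from prospective participants (Protocol 7.2) and records eligibility (12.1.1). Withdrawal can be the investigator's decision (7.4).

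**Balance and replacement.** Protocol 7.3 gives half of the participants each order, "with a possible maximum imbalance of 2". SAP 3.2 specifies permuted blocks of four without stratification. Protocol 7.4 keeps at least five already screened back-ups "to replace those that withdraw or are withdrawn". Neither document says which list entry a replacement receives, or whether back-ups are randomised when they are screened.

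**Analysis.** The primary Wilcoxon signed-rank test (Protocol 11.4.2, SAP 6.2.1) has no term for slot. It uses participants with primary outcome data, collected at visit 3, without imputation (Protocol 11.4.1 and 11.5).

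**The concern.** No visit 1 procedure needs the slot. Drawing it there means that anyone lost in the first field period has used a list place without ever receiving the music programs. Blocks of four balance the list, not the subset who return.

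Protocol 6.1.1 itself expects the earlier slot to score higher, because it is more prominent and some participants may not scroll to the third program. Randomising position is the planned answer to that effect, and the primary test does not adjust for it. The AMP order follows the same allocation (P2 at visit 2, P3 at visit 3), so an imbalance also enters the paired comparison of IP with SP there.

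The open list raises a separate point. The person who enrols, may withdraw participants and draws on the back-ups can see which slot comes next. The stated reason for single blinding, the investigator's part in fitting the IP, arises at visit 2 and does not require an open list at enrolment.

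**Working it through.** **Inputs from the documents:** blocks of four, two orders (SAP 3.2); N of 18-20 (Protocol 11.2, SAP 3.3); limit of 2 (Protocol 7.3); replacement of withdrawals (7.4). **Assumed:** the early loss rate and the list entry a replacement takes, because neither is given.

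**1. The plan's own figure.** Each complete block is balanced 2:2, so imbalance among those randomised comes only from the last, incomplete block. Over the six possible blocks the maximum is 0, 1, 2 and 1 for N mod 4 = 0, 1, 2 and 3. That gives 2, 1 and 0 at N = 18, 19 and 20. The limit of 2 is reproduced for those randomised.

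**2. Two cases by hand.**
- N=18 randomised, one early loss, no replacement. The list stands at 10:8 with probability 2/6. The limit is exceeded if the loss comes from the eight: 2/6 x 8/18 = 0.148, about 15%.
- N=19 fitted, two early losses, replacements on the next entries. Twenty-one are randomised, 11:10. The limit is exceeded if both losses come from the ten: 10/21 x 9/20 = 0.214, about 21%.

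**3. A fixed number of random early losses, replacements on the next entry.** Chance of imbalance above 2 among those fitted (simulation, 40,000 lists per cell):

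| N fitted | 1 loss | 2 | 3 | 4 | 5 |
|---|---|---|---|---|---|
| 18 | 0 | 0 | 9% | 14% | 16% |
| 19 | 0 | 21% | 28% | 32% | 32% |
| 20 | 0 | 7% | 10% | 9% | 16% |

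N=19 fares worse because an odd total passes the limit at 3, whereas an even total must reach 4. If the replacement inherits the vacated entry, every cell is 0.

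**4. An assumed early loss rate**, independent between participants, replaced from the next entry until N are fitted:

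| N fitted | 5% | 10% | 20% |
|---|---|---|---|
| 18 | 1% | 4% | 13% |
| 19 | 7% | 17% | 32% |
| 20 | 2% | 6% | 15% |

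With the draw at visit 2, all these entries become 0.

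**5. Effect on the result.** Let the slot effect be the shift in preference score towards whichever program is in slot 2. It enters with a plus sign when the IP is there and a minus sign when the SP is. The mean score then moves by (imbalance/N) x slot effect. At N=18 this is 2/18 = 0.11 of the slot effect at the permitted limit, and 4/18 = 0.22 at an imbalance of 4. The documents give no size for the slot effect, so this cannot be carried through to the test.

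**6. The analysed set.** With 10% early loss (next entry) and a further 10% unreplaced loss between visits 2 and 3, both assumed, the chance of imbalance above 2 at N=18 is about 19% with the draw at visit 1 and about 12% with the draw at visit 2.

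**7. Concealment.** With a hidden list and known blocks of four, the fourth entry of each block can always be deduced, and the third in two of the six blocks: (6 + 2)/24 = one third of entries. With the open list, all entries are known in advance.

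**The case against.** The strongest reply is that Protocol 7.3 is not wrong. It states a limit on how participants are assigned, and blocks of four meet that limit exactly. This stands. A reader might infer from the timing that drop-outs and replacements do break the limit; the documents support only that it can be exceeded, in a group (those fitted) for which no promise is made. The percentages also need the next-entry rule, which Protocol 7.4 neither states nor excludes; under the inherit rule they vanish without any change of timing.

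A reader might also infer that slot balance is the only safeguard. It is not. Every participant receives both programs and is told to use them equally (Protocol 8.2.1), gets an email reminder, and has hours per program logged (8.4). These measures act directly on the mechanism named in 6.1.1. If losses are random, the imbalance favours neither program systematically, and the trial is exploratory.

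It would also be wrong to say that the open list causes the imbalance; with random losses it does not. The investigator must in any case know the slot when tuning the IP, so nothing here conceals it after visit 2.

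The objection that a visit 2 draw fails to protect the analysis is only partly right. Later losses remain, but the chance of exceeding 2 among those analysed does fall (step 6).

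**Conclusion.** The point holds in a limited form, as a worthwhile refinement and not an error that threatens the trial. The slot is drawn one visit before it is needed, and the limit of 2 is guaranteed only for those randomised. Among those fitted, the chance of exceeding it ranges from about 1% (5% early loss, N=18) to about 32% (20% early loss, N=19). This rests on assumed, random early losses and on replacements taking the next entry; it is 0% if they inherit the vacated one. The effect on the primary result is modest because each participant compares both programs, but any slot effect that does carry over goes unadjusted. Advance sight of all allocations is a second, separate weakness, which these figures do not measure.

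**What to change.** Draw or reveal the slot at visit 2, once the participant's return is confirmed and just before the music programs are loaded. Have the statistician, or the data capture system, release one allocation at a time instead of filing the whole list with the investigator. Suggested wording for 6.1.1:

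> The position of SP and IP is allocated at visit 2, after the participant has returned and before the music programs are loaded. The statistician holds the list and releases the next entry for that participant only. The maximum imbalance of 2 refers to participants fitted with the music programs.

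The places to change are both copies of the schedule table (Study Schedule and 9.1), Protocol 6, 6.1.1, 6.2, 9.3.1 and 9.3.2, and SAP 3.2. Early drop-outs and unused back-ups then hold no list entry. One sentence in 7.4 should still say which entry is used if someone is replaced after visit 2.

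The cost is a release step at visit 2, plus system set-up and validation if it runs through the data capture system (Protocol 12.2.1). No visit, staff or participant burden is added. Two limits remain. Losses between visits 2 and 3 can still unbalance the analysed set, so a sensitivity analysis by slot order would be a useful complement. With fixed blocks of four, an investigator who knows the block size and past allocations could still deduce one third of entries, instead of seeing them all.

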#### **9.3.2 Fitting/Second visit**

Fitting Visit, Day 10 +/- 7: Otoscopy is performed, and the subjects return the completed questionnaires. The IMDs are fitted with IP and SP as specified by the randomization carried out at the first visit. The IP is optimized and fine-tuned based on comments that the subject makes about the sound while they play their instrument in the clinic. The SP is programmed without any adjustment based on the default music program offered in the software. They are instructed to switch between programs two and three when playing and listening to music for the next 10 +/- 7 days. They perform the lab test with the AMP in one condition: aided with P2. The subjects are given the music perception questionnaires and instructed to complete them at home a day before their next appointment. One questionnaire pertains to P2 and the other to P3. Any AEs are reported in the CRF. They are scheduled for the third visit.

#### **9.3.3 Lab/Third visit**

Final Visit, Day 20 +/- 7: Otoscopy is performed. The subjects return the completed product questionnaires. They perform the lab test with the AMP in one condition: aided with P3. They complete a preference questionnaire during the appointment. They are notified that the trial has ended and those that normally wear hearing aids can return to using their own devices. They will return the IMD to the clinic. Any AEs are reported in the CRF. Those that are on the Bernafon subject list and normally wear devices fitted by the Bernafon clinic are reminded to return to the clinic for normal maintenance of their hearing aids. Anyone that would like to join the Bernafon clinic are also welcome to do so.

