musical setup). For musicians the dedicated program may require further optimization and fine-tuning specific to their instrument and/or the situations in which they play music.

For this study, Bernafon AG will carry out testing with participants that are musicians with hearing loss to compare dedicated music programs. The current study will compare the standard music program available in the software to one that is fine-tuned for each participant. The Bernafon hearing aids used for the current study are CE- marked and have been on the market for almost one year. The goal is to determine whether musicians will perceive a difference and prefer a fine-tuned music program over the default music program in real-life situations.

The devices used for the trial are the Bernafon Viron 9 miniRITE (MNR) behind-the-ear (BTE) hearing aids. The results of the trial will be used to examine differences in the benefit provided by the two music programs as well as identify further optimization possibilities of the default music program provided by the fitting software. Objective measures will be made with Real Ear Measures (REM) to verify the output of the hearing aids, and subjective differences will be measured with questionnaires and an adaptive music perception test (Kirchberger & Russo, 2015).

All participants are hearing impaired persons that play an instrument. The trial will consist of a total 3 appointments. For the field testing and the lab testing, the order of the programs (optimized or default) will be randomized. It is expected that the optimized program will perform better than the default program for perception and preference testing.

In summary, the primary goal of this study is to evaluate the currently marketed hearing aids regarding their performance with music and to further validate the safety of the devices.

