## 9.2 Assessments of outcomes

### 9.2.1 Assessment of primary outcome

The primary outcome is the preference questionnaire. The hearing aids will be programmed with the two music programs, the SP with the standard default music settings and the IP with the optimized fine-tuned music settings. The subjects will use both programs during the second field test and then be asked to choose a preference for listening to music and/or when playing music. The questionnaire also asks that they rate how sure they are of their choice on a 10-point scale with 10 being completely sure and gives a list of reasons for the choice from which they can select as many as they choose.

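### Protocol 9.3.3 lists the P3-only lab test before the primary preference questionnaire and does not fix the order; taking the preference first would remove an avoidable source of noise at no cost

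*Protocol*

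**What the plan says.** **Visit 3.** After otoscopy and the return of questionnaires, Protocol 9.3.3 continues: "They perform the lab test with the AMP in one condition: aided with P3. They complete a preference questionnaire during the appointment". The schedule in Protocol 9.1 ticks both procedures at visit 3 and sets no order between them.

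**The matching P2 test.** It takes place one field period earlier. Protocol 9.3.2 has: "They perform the lab test with the AMP in one condition: aided with P2". Protocol 7.3 confirms the pattern: "The subjects will perform the lab test with P2 at visit 2 and P3 at visit 3".

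**What the preference should capture.** Protocol 3.1 gives the goal as whether musicians "prefer a fine-tuned music program over the default music program in real-life situations". Protocol 9.2.1 says: "The subjects will use both programs during the second field test and then be asked to choose a preference". The field exposure comes from 9.3.2: "They are instructed to switch between programs two and three when playing and listening to music for the next 10 +/- 7 days".

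**Allocation and blinding.** IP and SP are randomised to slots P2 and P3, about half each way, with a maximum imbalance of 2 (Protocol 7.3). The list uses permuted blocks of four (SAP 3.2). Participants do not know which slot holds which program (Protocol 6).

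**Analysis.** The five-point preference score is tested with a Wilcoxon signed-rank test that has no term for slot (Protocol 11.4.2, SAP 6.2.1). The test is two-sided at 0.05 (SAP 4.1). The sample size is 18 to 20, and the SAP states that no effect size could be estimated (SAP 3.3).

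**The concern.** A site following 9.3.3 in the order written would run the AMP through P3 and then ask the participant to rate P2 against P3. The AMP is a two-alternative forced-choice task with a two-down, one-up rule (Protocol 9.2.2). It covers meter and timbre with three dimensions each (SAP 6.1.4). A session of that kind could leave a fresh impression in favour of P3, or tiredness and frustration that count against it. Either would enter the primary score, although that score is meant to summarise the preceding field period.

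The plan already handles a secondary measure differently. The music perception questionnaires for P2 and P3 are filled in at home the day before the visit (Protocol 9.3.2), so before that day's AMP. The primary measure has no such protection. At stake is some precision in a test on 18 to 20 people and, under particular conditions, a small shift in the mean score.

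**Working it through.** **1. Is the order fixed?** Protocol 9.3.3 lists the AMP first and says only that the preference is completed during the appointment. No section of either document places the preference before the AMP, adds a pause, or has both programs heard again first. The order is therefore implied by the listing and otherwise open.

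**2. Slot imbalance (the plan's own figure).** Six blocks of four contain two of each order. Enumerating them gives a largest imbalance of 2 at any point, which reproduces Protocol 7.3. At n=20 the final imbalance is 0, and at n=19 it is 1. At n=18 the last block contributes two participants. They share an order in 2 of the 6 blocks, so a 10/8 split has probability 1/3.

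**3. Direction of an equal carry-over.** Let r be the pull towards P3, and score in favour of IP. The mean shift is r × (n with IP in P3 − n with SP in P3) / n.
- Balanced slots: r × 0 = 0.
- 10/8 at n=18: r × 2/18 = r/9. That is 0.056 for r=0.5 and 0.083 for r=0.75. After rounding to the five categories, simulation gives 0.049 and 0.077 on a scale from −2 to 2.
- As a share: if 70% chose P3 from recency alone, the expected IP share would be 50% with balanced slots. At 10/8 it would be (10 × 0.7 + 8 × 0.3)/18 = 9.4/18 = 52.2%.

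**4. Unequal carry-over.** Let the pull towards P3 be a when P3 holds IP and b when it holds SP. With balanced slots the mean shift is (a − b)/2, which is zero only if a = b. For illustration, a = −0.5 and b = 0 give −0.25. The documents give no values for a or b. The IP is tuned while the participant plays their own instrument (Protocol 9.3.2) and the AMP uses recordings (Protocol 5.2), so equality is plausible but not assured.

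**5. Power.** The documents give no carry-over size, effect size or variance, so every input here is assumed. Set-up A: latent normal preference with SD 1.2, rounded and clipped to −2 to 2; IP shift 0.85; n=20 with slots 10/10; signed-rank test with zeros dropped and normal approximation; 6,000 runs. The equivalent sample loss is 1 − 1.44/(1.44 + r²).

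| Pull r (points) | Power | Equivalent sample loss |
|---|---|---|
| 0 | 0.824 | 0% |
| 0.25 | 0.809 | 4% |
| 0.5 | 0.761 | 15% |
| 0.75 | 0.692 | 28% |

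The simulation standard error is about √(0.82 × 0.18/6000) = 0.005 per figure, so the step from 0 to 0.25 is barely distinguishable from no loss.

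Set-up B varies the assumptions: SD 1, cut-points ±0.4 and ±1.25, IP effect 0.7 SD, 4,000 runs, balanced slots.

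| Pull (SD) | Power n=18 | Power n=20 | Type I error n=18 |
|---|---|---|---|
| 0 | 0.75 | 0.82 | 0.045 |
| 0.25 | 0.74 | 0.79 | 0.042 |
| 0.5 | 0.67 | 0.74 | 0.029 |
| 1.0 | 0.42 | 0.47 | 0.005 |

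At 10/8 the type I error stays at or below 0.046 over the same range of pulls.

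**The case against.** The best case against acting is that there may be almost nothing to correct.

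- **Sequence.** A reader might infer that the preference is taken straight after the AMP. The text does not say so. Listing order in Protocol 9.3 is weak evidence: 9.3.3 also lists device return before adverse event recording. This stands, and the point is therefore limited to an order that is listed but not fixed.
- **Exposure.** P3 is the only program tested in the lab that day, but participants have switched between both programs for 10 ± 7 days. They took the same AMP with P2 at visit 2, and recorded impressions of both programs at home the day before. This stands, and makes a large carry-over less likely.
- **Bias.** A reader might infer that the P3 session tilts the result towards IP or SP. Slot randomisation prevents that for an equal carry-over. Only the residues in steps 3 and 4 of the working remain.
- **Size.** Pulls of 0.5 and 0.75 points are 59% and 88% of the assumed 0.85 IP shift, which is large for one session of a threshold task. At 0.25 points the loss is slight. This stands: the figures show sensitivity and do not forecast an effect.
- **Separability.** A reader might count it as a further harm that lab carry-over cannot be told apart from the scroll-position effect named in Protocol 6.1.1. Separating two nuisance effects is no objective of the trial. The case report form records slot (Protocol 12.1.1), so their combined effect can be examined.

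None of this gives a reason to keep the AMP first. The AMP does not depend on a preference rating having been withheld.

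**Conclusion.** The point holds in a limited form. As listed, the primary preference follows a same-day lab session heard through P3 only, and nothing places it first, although it is meant to describe field use of both programs.

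With slots balanced and carry-over equal for IP and SP, the consequence is noise. In set-up A, power falls from about 82% to 81%, 76% or 69% for pulls of 0.25, 0.5 and 0.75 points, and in set-up B type I error does not rise. The bias from a 10/8 split is about 0.05 to 0.08 points for pulls of 0.5 to 0.75. Dropouts could unbalance slots further, and carry-over that differs between IP and SP would add (a − b)/2.

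The size and direction of any real carry-over are unknown, and it may be absent. In a study that calls itself exploratory this does not threaten validity. It is worth changing because the change is free.

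**What to change.** Add one sentence to Protocol 9.3.3: the participant completes the preference questionnaire on arrival at visit 3, before the AMP test and before any switching of programs in the clinic; the AMP with P3 follows. The primary score then rests on the field period, as Protocol 3.1 and 9.2.1 intend, and any disturbance from that day's AMP is removed.

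The cost is the reordering of two procedures within one visit. Forms, staff, visit length, sample size and the planned test stay the same.
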